# LIST OF ABBREVIATIONS AND RELEVANT DEFINITIONS

ABR AE	ABR form (General Assessment and Registration form) is the application form that is required for submission to the accredited Ethics Committee (ABR = Algemene Beoordeling en Registratie) Adverse Event
AR CA CCMO CV	Adverse Reaction Competent Authority Central Committee on Research Involving Human Subjects Curriculum Vitae
DSMB EU	Data Safety Monitoring Board European Union
EU EudraCT IB	European drug regulatory affairs Clinical Trials GCP Good Clinical Practice Investigator's Brochure
IC	Informed Consent
	Investigational Medicinal Product
IMPD METC	Investigational Medicinal Product Dossier
MEIC	Medical research ethics committee (MREC); in Dutch: medisch ethische toetsing commissie (METC)
(S)AE	Serious Adverse Event
SPC	Summary of Product Characteristics (in Dutch: officiële productinfomatie IB1-tekst)
Sponsor	The sponsor is the party that commissions the organisation or performance of the research, for example a pharmaceutical company, academic hospital, scientific organisation or investigator. A party that provides funding for a study but does not commission it is not regarded as the sponsor, but referred to as a subsidising party.
SUSAR	Suspected Unexpected Serious Adverse Reaction
Wbp	Personal Data Protection Act (in Dutch: Wet Bescherming Persoonsgevens)
WMO	Medical Research Involving Human Subjects Act (Wet Medisch- wetenschappelijk Onderzoek met Mensen

#### SUMMARY

**Rationale:** To improve the rate of use of prosthetic devices in adults with an upper limb amputation intermanual transfer might be helpful. Intermanual transfer is the ability to transfer motor skills from one, trained side to the other side (Hicks, 1983). This can be used in upper limb amputees by training the unaffected arm while waiting for the prosthesis to be fitted. Especially because it is assumed that training starting early after the amputation will lead to better acceptance and improved prosthetic handling (Malone, Fleming et al. 1984). Due to intermanual transfer, the prosthetic skills of the affected arm will then improve. Intermanual transfer effects were demonstrated to be present in myo-electric (Romkema, Bongers et al. 2013) and body-powered prosthesis use (Weeks, Wallace et al. 2003). However, it is unclear how the training program should be like to obtain the largest effects. The question rises how the training should be spaced over time for the best results.

**Objective**: To compare different training intensities to be able to measure which training has the largest effects.

Study design: non-blinded randomized trial.

Study population: 64 non-amputated adults.

**Intervention (if applicable)**: Four groups of 16 participants train to use a prosthetic simulator for 20 min during 5 days and are tested on their skills with a prosthetic simulator. The prosthetic simulator mimics the functioning of a real prosthesis but can be worn by ablebodied participants and at the sound side of an amputee patient. The prosthesis simulator places a prosthetic hand in front of the sound hand.

#### Main study parameters/endpoints:

- Grip force control: mean deviation of the asked force in N.
- Reaching: mean deviation of the straight path towards the aim in mm
- Grasp: shape of the grasp profile; plateau duration in s.
- Movement time: time taken to execute the movement in s.

# Nature and extent of the burden and risks associated with participation, benefit and group relatedness:

All participants will use the prosthetic simulator. This simulator mimics a real prosthetic device and can be worn over a sound arm. Because of the use of this simulator we are able to test more participants than only the few recently amputated patients. Importantly, all the measurements are non-invasive and the use of a prosthetic simulator is not different from wearing a regular prosthesis. Therefore, the risks associated with participation can be considered negligible and the burden can be considered minimal.

#### 1. INTRODUCTION AND RATIONALE

To improve the rate of use of prosthetic devices in adults with an upper limb amputation we have been using intermanual transfer. Intermanual transfer implies that when you learn a motor task with one arm, not only that arm improves, but also the arm at the other side becomes better in the specific task (Hicks, Gualtieri et al. 1983, Karni, Meyer et al. 1998, Kumar, Mandal 2005, Lee, Hinder et al. 2010, Mier, Petersen 2006, Pereira, Raja et al. 2011). The untrained side thus benefits from the trained side. In other words, the effect of intermanual transfer is that the prosthetic skills of the affected arm will improve. The intermanual transfer effect is shown to be present in body-powered (Weeks et al., 2003) and also in myo-electric prostheses (Romkema, Bongers et al. 2013). With able-bodied participants we showed that after training the 'unaffected' side using a prosthesis simulator, the level of skills at the 'affected' side increased. This effect can be useful in rehabilitation after an upper limb amputation, because the training can be started earlier. It is assumed that training immediately after the amputation will lead to better acceptance and prosthetic handling (Malone, Fleming et al. 1984). It is found that training should start within one month after the amputation to achieve maximum success (Atkins 1992, Dakpa, Heger 1997, Gaine, Smart et al. 1997). Though in this period often the wounds are not healed yet and the prosthesis is not finished. Using a prosthetic simulator the training at the sound side can start early what might lead to better acceptance and higher prosthesis skills due to effects of intermanual transfer. This might decrease rejection rates of prosthesis devices rejected.

To be able to train the unaffected arm we make use of a prosthetic simulator. With this simulator it is possible to mimic a myo-electric prosthesis. A prosthetic hand can be opened and closed with a motor driven by electrical signals that are produced by muscle activation. The simulator is placed over the arm, and the prosthetic hand is placed before the sound hand (Figure 1) and then operates in the same way as the prosthesis. The training with the simulator is therefore comparable to the training with the myo-electric prosthesis.

In our earlier study (Romkema, Bongers et al. 2013) where we demonstrated the effect of intermanual training in prosthetic learning we used functional tasks. We found that the movement times increased after a five-day training program.

We now would like to optimize the spacing of the training program. It is generally known that variations in spacing affect the effectiveness on training (Kornmeier, Sosic-Vasic 2012, Donovan, Radosevich 1999, Schmidt, Lee 2005, Shea, Lai et al. 2000) For instance, Donovan (1999) found in a meta-analyses of 63 studies, that training in spaced practice conditions leads to significantly higher performance than training in massed practice conditions. Literature on the spacing of training sessions is mostly focused on intertraining periods within 24 hours. Because in this literature the longer intervals (i.e., up to 24 hours) are found to have the largest effects (Siengsukon, Boyd 2009, Kornmeier, Sosic-Vasic 2012, Shea, Lai et al. 2000, Goedert, Miller 2008, Hussain, Sekuler et al. 2009) and because such intertraining time intervals are realistic for rehabilitation we will use intervals of at least 24 hours. It is currently unknown what the effect is of longer time intervals. The current study will examine these longer time intervals because in rehabilitation practice they are often more practical. In an earlier pilot of our group, measuring three people training with the simulator in different intervals, we found the largest effect on the every-day training. This suggests that we might get the largest effect with an every-day training.

In conclusion, with this study we aim to optimize the intermanual transfer effects in prosthetic use that we have shown to be present in earlier research. For this we compare different time intervals between training sessions (i.e., spacing of the training). This research will be done with able-bodied participants. Including able-bodied participants will mean that we do not have to bother patients who have just been amputated.

# 2. OBJECTIVES

The objective of our study is to compare different training intensities to be able to measure what training has the largest effects.

# 3. STUDY DESIGN

The experiment aims to reveal the effect of spacing on the intermanual transfer. As found in the available literature, for different tasks, the largest effects are found with a period of minimally 24 hours, the longest period that is tested, between training sessions. Though, the topic of spacing has not received a lot of attention in training motor skills and for periods longer than 24 hours. The sparse evidence revealed that the optimal training effects depend on the nature of the task and on the combination of time interval between the training and the time till the retention test. For this study we therefore choose to use two different time intervals with a minimum of 24 hours. The first group trains daily, the second group trains with two and three days intervals between the training sessions. The training tasks will be chosen based on the previous experiment; the tasks with the largest effects will be used. Two control groups are added both following one of the training shemes of the training groups. These groups will execute a sham training where the wrist muscles are used though the prosthesis is not worn. The tests consists of a pretest, posttest and retention test (seven days after ending the training), to be able to measure whether there were learning effects and whether these effects remained (see 7.3 for an extensive explanation). All tests consist of the same tasks; functional, grip force control, reaching and grasping tasks. Half of the

participants will train their dominant hand and half will train their non-dominant hand. Apart from the three tests, as used in the last experiment, there will be an extra retention test. The first retention test takes place on day 17, so that the first retention test is at the same time interval after the first training for all the spacing regimes. The second retention test is conducted two weeks after the last training session. This will make it possible to show the effects of the different intervals till two weeks after the training.

Healthy adults		i		_				
Spacing	Short inter	rval	Short cont	trol	Long interv	val	Long Cont	trol
Participants	8 men, 8 women (½ dom, ½ n-dom)		8men, 8 women (½ dom, ½ n-dom)		8 men, 8 women (½ dom, ½ n-dom)		8 men, 6 women dom, ½ n-dom)	
Day	Test	Practice	Test	Practice (sham)	Test	Practice	Test	Prac (sha
1 (Mon)	Pretest	30 min	Pretest	30 min	Pretest	30 min	Pretest	30 n
2 (Tue)		30 min		30 min				$\Box$
3 (Wed)		30 min		30 min				
4 (Thurs)		30 min		30 min		30 min		30 n
5 (Fri)	Posttest	30 min	Posttest	30 min				$\Box$
8 (Mon)						30 min		30 n
9 (Tue)								$\top$
10 Wed)					T	 	 	
11 (Thurs)						30 min		30 n
12 (Fri)								Τ
15 (Mon					Posttest	30 min	Posttest	30 n
16 (Tue)								
17 (Wed)	Retention test		Retention test		Retention test		Retention test	
19 (Fri)	Retention test		Retention test					
24(Wed)								
29 (Mon)					Retention		Retention	+
					test		test	

Table 2	Study	design	of the	second	experiment	on spacing
10010 2.	Clady	acoign		0000110	onportation	on optioning

# 4. STUDY POPULATION

# 4.1 Population (base)

64 non-amputated adults

#### 4.2 Inclusion criteria

- (1) Normal or corrected to normal sight
- (2) Right-handed
- (3) Aged 18 till 40

# 4.3 Exclusion criteria

- (1) Neurological problems concerning upper extremity or torso
- (2) Motor problems concerning upper extremity or torso

- (3) Earlier experience with a prosthetic simulator
- (4) Limited sight despite correction

# 4.4 Sample size calculation

For the second experiment the sample size calculation is done based on the data a previous experiment. The test tasks of the experiment are also used in the first experiment. The participants of both experiments will train on 5 days. We used the pretest and retention test of the force control task to decide what the expected differences are. Using g power we made an estimation of the amount of participants necessary within each group to reach a power of 0.8. Here for we used single side testing with an alfa of 0.05.

Because of the changes for this experiment we can not give an exact estimation. The training will be longer and the tests shorter. We therefore expect the effects to be larger. Though, because we do not have different training tasks but only a difference in spacing we would expect the differences to be smaller.

With the described method we found that we need to have 17 participants in each group (table 5). We would like to make this 16 participants to get an equal distribution of men/women and dominant/not dominant test hand per group.

#### Tabel 5

Sample size per group

		power	pretest	retentietest
Task	Effect size	0.8	deviation	Deviation
Force control	.89	17	7.39	5.04

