#### 10.4 Analysis (if applicable)

In the experiments all measurements (deviation of grip force control, deviation of straight reaching path, length of plateau phase in grasping and movement time) are subjected to a repeated-measures ANOVA with test (pre-test, post-test and retention test(s)) as within-subject factor and dominance (preferred, non-preferred) and group (two experimental groups, two control groups) as between-subject factors.

When a Mauchly test indicates that sphericity is violated, the degrees of freedom are adjusted with the Greenhouse-Geisser correction. In all analyses, a significant criterion of  $\alpha$  less than or equal to 0.05 is used, and post hoc tests on main effects use Bonferroni adjustment.

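### The power of 0.8 in Section 4.4 comes from a one-sided two-group calculation and does not belong to the non-directional repeated-measures ANOVA with Bonferroni post hoc tests planned in Section 10.4

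*Protocol*

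**What the plan says.** Section 4.4 of the protocol holds the only power statement. The effect size comes from an earlier experiment: "We used the pretest and retention test of the force control task to decide what the expected differences are". The group size is the number "necessary within each group to reach a power of 0.8", and on the error rate the section says "Here for we used single side testing with an alfa of 0.05". The row of its table reads "Force control .89 17 7.39 5.04": effect size 0.89, 17 per group, pretest deviation 7.39, retention deviation 5.04. The test chosen in the software is not named, and no standard deviation or correlation is given. The section then lowers the number: "We would like to make this 16 participants to get an equal distribution of men/women and dominant/not dominant test hand per group". The Summary confirms the size: "Four groups of 16 participants train to use a prosthetic simulator".

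Section 10.4 sets out the analysis. Each of the four outcomes goes into a repeated-measures ANOVA. Test occasion is the within-subject factor; hand dominance and group (two experimental, two control) are between-subject factors. The criterion is 0.05 throughout, and "post hoc tests on main effects use Bonferroni adjustment". No one-sided test is mentioned and no number of comparisons is stated.

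**The concern.** A power figure describes one particular test. Here the figure was computed for a directional comparison of two groups, while the analysis has four groups, F-tests without direction and a multiplicity adjustment after them. Sidedness and adjustment both make significance harder to reach than the calculation assumes.

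The purpose of the trial is to compare spacing schedules. If the spacing comparison is not significant, readers will judge that result against a stated 80% chance of detecting the effect. That 80% was never worked out for the test that produced the result.

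**Working it through.** **Inputs.** From Section 4.4: d = 0.89, one-sided alpha 0.05, target power 0.8, 17 per group calculated, 16 planned. From Section 10.4: four groups, alpha 0.05, Bonferroni post hoc. Four groups give 4 × 3 / 2 = 6 pairs; this divisor is derived, not stated. Withdrawals are replaced (Section 8.5), so no dropout allowance is applied.

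**Formula.** For two independent groups of n, power is the probability that a noncentral t variable with 2n − 2 degrees of freedom and noncentrality d × √(n/2) passes the critical value.

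**Reproducing the 17.**
- n = 17: noncentrality 0.89 × √8.5 = 2.59, one-sided critical t (32 df) 1.694, power 0.81.
- n = 16: noncentrality 0.89 × √8 = 2.52, one-sided critical t (30 df) 1.697, power 0.79.

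So 17 is the smallest exact n with power 0.8. The other candidates do not give 17: two-sided two-group needs 21; a paired t-test needs 10 one-sided or 12 two-sided. The one-sided two-group t-test is therefore inferred from an exact match.

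**One pair of groups, one occasion, d = 0.89, 16 per group.**

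| Test | Alpha | Critical t (30 df) | Power |
|---|---|---|---|
| One-sided | 0.05 | 1.697 | 0.79 |
| Two-sided | 0.05 | 2.042 | 0.68 |
| Two-sided, three contrasts | 0.05/3 = 0.0167 | 2.536 | 0.50 |
| Two-sided, six pairs | 0.05/6 = 0.0083 | 2.825 | 0.40 |

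With the pooled error of the four-group, two-dominance layout (64 − 8 = 56 df), the two-sided figure is 0.70 and the six-pair figure 0.42. Power 0.8 would need 21 per group two-sided, or 33 with six pairs.

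**What the ANOVA adds.** Whether spacing changes learning is a test-by-group question. For a pairwise contrast of change from pretest, with equal variances and correlation r between the two tests, the SD of the change is SD × √(2(1 − r)). The effective size is then 0.89 / √(2(1 − r)):

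| Assumed r | Effective d | Two-sided power, 16 per group |
|---|---|---|
| 0.3 | 0.75 | 0.54 |
| 0.5 | 0.89 | 0.68 |
| 0.7 | 1.15 | 0.88 |
| 0.8 | 1.41 | 0.97 |

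This column carries no Bonferroni adjustment. The values of r are assumptions.

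**Detectable difference at 16 per group, power 0.8, single occasion.** d = 0.90 one-sided, 1.02 two-sided, 1.31 two-sided with six pairs. If 0.89 is the tabled difference over an SD, that SD is (7.39 − 5.04) / 0.89 = 2.35 / 0.89 = 2.64 N. The last two then become 1.02 × 2.64 = 2.7 N and 1.31 × 2.64 = 3.5 N. The protocol does not say how 0.89 was formed, so the newton values hold only on that reading.

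**The case against.** The strongest reply is that 0.68 and 0.40 are not the power of the planned analysis either. They ignore the pretest and the repeated measurements. With a correlation of 0.7 or more, the two-sided change contrast exceeds 0.8 before any Bonferroni adjustment. This stands: the figures must be labelled as pairwise and single-occasion, and the range over r must be shown. A reader might infer that the trial has been shown to have less than 80% power. The protocol does not support that, because it gives no correlation.

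The six-pair divisor is also an inference. Section 10.4 applies Bonferroni to main effects only, and the group main effect averages over all occasions, including the pretest, so d = 0.89 is not strictly its effect size. This stands too; 0.40 is conditional.

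A reader might further infer that the protocol has no basis for a direction. That goes too far. The literature in Section 1 that favours longer intervals covers intervals up to 24 hours. Beyond that the section calls the effect unknown and offers one expectation, that daily training may do best, from a three-person pilot. The basis is weak, but a direction is expressed, and the cited literature does not contradict it. Even so, Section 10.4 does not carry that direction into any test.

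Finally, Section 4.4 admits that its estimate is not exact and openly explains the move from 17 to 16. That move costs only about 0.02 (0.81 to 0.79). The disclosure is fair, but it concerns the likely effect, not the mismatch of tests.

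**Conclusion.** The mismatch is real and lies within the protocol: Section 4.4 and Section 10.4 describe different tests, and the only stated power belongs to the one that will not be run. For a single-occasion comparison of two groups, two-sided testing alone takes power from 0.79 to 0.68 (0.70 with pooled error). Bonferroni over six pairs, if that is what is meant, takes it to about 0.40 to 0.42; three contrasts give 0.50. All of this assumes that 0.89 applies as a between-group effect.

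The power of the test-by-group interaction cannot be fixed from the document. For the change contrast, 0.54 to 0.97 is the range for r from 0.3 to 0.8. The conclusion is that the 0.8 is unsupported for the planned analysis, not that the true power is any one of these numbers.

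The effect size adds further doubt. It comes from pretest and retention data of an earlier experiment. Section 4.4 expects smaller differences when only the spacing varies, although it also expects larger effects from longer training and shorter tests. As an illustration, an assumed d = 0.6 gives pairwise power of 0.38 two-sided and 0.15 with six pairs.

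**What to change.** Keep 64 participants and the analysis in Section 10.4, and correct Section 4.4:

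- Remove the one-sided basis, and name the comparison that the power refers to and the Bonferroni divisor that applies to it.
- Replace the unqualified 0.8 by two-sided power at 16 per group for that comparison: 0.68 for a single-occasion pair, the range 0.54 to 0.97 over assumed r of 0.3 to 0.8 for change from pretest, and the Bonferroni figure for the chosen divisor.
- Alternatively, state the detectable difference: d = 1.02 two-sided, or 1.31 with six pairs. Give 2.7 N and 3.5 N only if 0.89 is confirmed to be 2.35 N over the SD.
- State that 0.89 comes from pretest and retention data of a previous experiment, and keep beside it the section's own expectation that spacing differences will be smaller.

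The cost is rewording. The stated power becomes less favourable; no participants are added, and conduct does not change.

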# 5. TREATMENT OF SUBJECTS

#### 5.1 Investigational product/treatment

The participants learn to use the prosthetic simulator during training sessions. These sessions take place on five days to promote learning. Each training session will take thirty minutes.

5.2 Use of co-intervention (if applicable) Not applicable 5.3 Escape medication (if applicable)

Not applicable

- 6. INVESTIGATIONAL MEDICINAL PRODUCT Not applicable
- 7. NON-INVESTIGATIONAL PRODUCT Not applicable

# 8. METHODS

8.1 Study parameters/endpoints

#### 8.1.1 Main study parameter/endpoint

- Grip force control: mean deviation of the asked force in N is measured in the grip force control tasks.
- Reaching: mean deviation of the straight path towards the target in mm is measured in the reaching task.
- Grasp: length of plateau phase (maximal hand opening) in seconds is measured in the grasping task.
- Movement time: time taken to execute the movement in seconds is measured in the functional task.

# 8.1.2 Secondary study parameters/endpoints (if applicable)

Not applicable 8.1.3 Other study parameters (if applicable)

Not applicable

# 8.2 Randomisation, blinding and treatment allocation

The able-bodied adults will be randomly assigned to one of the four groups (experimental and control groups). The number of participants that train with their dominant and non-dominant hand will be equal for both sexes.

#### 8.3 Study procedures

Prior to the start of the experiment all participants sign an informed consent and it will be explained to them that they can stop with the experiment at any time, without giving a reason.

The training program that shows the best results in an earlier study will be used for this experiment. Here only the intensity of the training will be changed over the different groups.

In the experiment the training and test tasks focusing on the same aspects differ from each other. This is to resemble a rehabilitation setting. Not only a single task but the prosthetic skill needs to be learned. In choosing the tasks for the training and test sessions we also take into account the complexity. A relative complex task is used for the training because then the effects on the other arm (of a simpler task) are assumed to be more prominent.

#### Materials 1

The myo-electric simulator is developed to closely resemble a myo-electric upper extremity prosthesis for a below-elbow amputation (see Figure 1). The simulator consists of a myo-electric hand, the MyoHand VariPlus Speed® of Otto Bock, attached to an open cast in which the hand can be placed. The cast extends into a splint along the forearm, adjustable in length. The splint can be attached to the arm using a selfadhesive (Velcro) sleeve. The prosthetic hand has proportional speed control (15-399 mm/s) and proportional grip force control (0-±100 N). The hand is controlled by changes in electric muscle activity, detected by 2 electrodes that are placed on the extensors and flexors in the forearm. The exact positions of these electrodes are determined after palpation of the most prominent contraction of muscle bellies of the extensors and flexors. Subsequently, these locations are marked to place the electrodes. The position of the electrodes is then optimized using Otto Bock PAULA®. Hand opening is accomplished by activity of the extensors, while the hand is closed by activity of the flexors. To mimic the use of a prosthesis as closely as possible, the participants are instructed to make minimal movement with the hand, because when one is amputated, the muscles can contract only isometrically.

Figure 1 a, b and c. The myo-electric simulator, dorsal, volar side and the electrodes inside.

Otto Bock Paula® (Figure 2) is used in conjunction with 757M11 MyoBoy® with USB connection to a PC for the fitting of the electrodes of the simulator. PAULA stands for Prosthetists' Assistant for Upper Limb Architecture, and is used by prosthetists to evaluate myo-signals and further selection and design of the prosthesis.

[figure not shown]

Figure 2. PAULA software on the computer screen, displaying myo-electric signals.

